The short term effects of transcranial neuromodulation are typically assumed to be mediated by increasing or decreasing of cortical excitability. The longer term effects appear to reflect stable changes in cortical plasticity, including long term potentiation (LTP) and long term depression (LTD) as evidenced by learning effects that are mediated by NMDA (Monte-Silva et al., 2013). The rationale of the present interventions is that inducing long term depression in the epileptogenic zone will be effective in suppressing seizures. However, the scientific understanding of this manipulation is limited, such that there is risk of changing plasticity in ways that are unwanted or maladaptive.

Mitigating the Risk of Unwanted Plasticity

In addition to manipulating epileptiform activity, the GTEN treatment may change other aspects of the patient's cortical function that may create unwanted changes in brain function or plasticity. The large general literatures for tDCS and slow rTMS suggest there are unlikely to be serious unwanted changes. Nonetheless, we will achieve more focal and potentially more effective current delivery than in previous research with tDCS, and we will achieve deeper current delivery than previous research with slow rTMS.

The primary effect on the target brain region is expected to be the induction of long term depression. We will evaluate general cognitive function in each patient with scores on the California Verbal Learning Test, paying close attention to any changes from the expected improvement in performance with practice from the normative data. The patient's baseline performance with the CVLT is assessed during the pre-treatment baseline assessment. We will also review the Quality Of Life In Epilepsy ratings and the seizure diary with each patient and family, systematically reviewing any complaints or reports that may suggest the treatment is creating unwanted changes in brain function. Finally, for each patient we will examine the effective dose delivered to non target brain regions as a function of the DCSV targeting recorded by the GTEN Planning Module to insure that the electrical dosage (and the presumed induction of long term depression) is appropriately limited to the target cortex.

Pre-Clinical Testing with Normal Volunteers

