However, the effective modulation of brain activity may depend not on the absolute current density, but on the current flow that is normal to the cortical surface. This is because the neurons of the cortex are aligned perpendicular to the cortical surface, and the induced current serves to alter neuronal polarization along the apical dendrite to somatic axis of the cortical pyramidal neurons (Datta, Zhou, Su, Parra, & Bikson, 2013). Wagner et al (2004) point out that as little as 30% of the current induced by TMS may be oriented normal to the cortical surface. This implies that TEN, which can be directed from the 256 channel array to be oriented mostly normal to the cortical surface, may achieve effective dosage that is within a factor of 10 less than the magnitude of the effective TMS induced current.

Importantly, a major advantage of TEN over TMS is the ability to reach deep sources. In the simulations of TMS by Wagner, et al. (2004), the depth penetration of TMS was 2 cm into brain tissue, where it reached only the crown of the gyrus, and there the current was largely tangential to the gyral crown (rather than surface normal). We must assume, therefore, that the targeting in the existing studies of slow rTMS for epilepsy (Fregni, et al., 2006; Sun, et al., 2012) was highly approximate. Although Fregni et al. used focal cortical dysplasias to guide targeting, it is highly unlikely that these were all within 2 cm of the cortex, or that effective targeting of current direction was achieved.

Therefore, considering these several factors, we can reasonably expect that the electrical dosage of the GTEN 100, with the safety and comfort level set at $200 \mu\text{A}$ per electrode for the study protocol pulses (**Figure 10**), when targeted appropriately to the epileptogenic focus with the 256 array and the high resolution head model, will be an effective treatment for seizure suppression.

Clinical Feasibility Trial Design

The goal of this unblinded and uncontrolled (“open-label”) feasibility study is to evaluate the safety, comfort, and preliminary efficacy of GTEN 100 treatment in achieving temporary suppression of epileptic activity, as assessed primarily by spikes and secondarily by seizures. The GTEN 100 applies small, electrical currents (up to $200 \mu\text{A}$ per electrode and up to 2 mA total) in a pattern that targets the cortical site of epileptiform discharges in order to decrease the excitability of the epileptogenic cortical tissue.

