The probe treatment and evaluation protocol is thus a subset (one block instead of 3 blocks of 17-minute pulses) of the approved treatment protocol.

The same GTEN Planning Module is used to develop each probe treatment targeting plan, with the primary difference being the cortical region that is targeted. This is a judgment made by the scientists (Drs. [name] and [name] at EGI) on the basis of the ability to target the cortical region, which is very difficult in medial temporal regions, and the epileptologist ([name] at Harborview) on the basis of the likely relation of the spike development to seizure onset. Often there are multiple possible targets, and the probe treatments and evaluations may allow us to contrast their efficacies.

Treatment Protocol

A two hour GTEN treatment session then targets the identified focal epileptogenic zone for 5 days during one week. For the first ten patients the post treatment monitoring is continued for 3 hours after the treatment session. For those patients whose spikes were more frequent during sleep during the baseline evaluation sessions, an effort will be made to have them fall asleep as the lidocaine takes effect and before the GTEN treatment begins, so that the treatment matches the excitable state during which spikes occur.

All sessions are conducted by personnel who are trained in the dEEG and GTEN 100 operation, including the ability to recognize epileptiform discharges in the dEEG signals. At least one person on the research staff at each session will be certified in first aid in the case that a seizure occurs. The epileptologist at each trial site will provide medical supervision, including recognition of possible adverse events and decision to terminate treatment.

Follow up Protocol

The one week treatment period is followed by a weekly seizure diary review by phone with the study coordinator for six months, plus a dEEG follow up evaluation session in weeks 2, 4, 8, 16, and 24. Each follow up session includes dEEG evaluation during the entire session, including during the review of seizure diary, cognitive function testing with the California Verbal Learning Test, and the Quality of Life in Epilepsy report, as well as a resting dEEG interval. If the patient has interictal events in sleep or drowsiness, the resting dEEG evaluation will include a quiet period for a nap.

Primary Endpoint and Study Success

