The primary endpoint is a temporary suppression of epileptic spikes. With assessments of spike rates at weeks 2, 4, 8, 16, and 24, the study will allow estimation of how temporary a suppression is achieved by the one-week treatment. The routine dEEG sessions typically collect dEEG for over an hour, and spike rates per hour will be the standard metric. To be successful, and to warrant progression to a randomized clinical trial, this clinical feasibility study must demonstrate successful targeting and suppression of the epileptogenic zone, as evidenced by temporary but statistically significant spike suppression in contrast to the pre-treatment baseline. All spike rates (baseline, treatment, and follow-up) will be counted as spikes per hour and classified in relation to waking or sleep stage (N1, N2, N3).

Secondary Endpoints and Study Success

The secondary endpoint is monthly suppression of seizures, assessed by the seizure diary each month for six months following treatment, in comparison to the mean seizure frequency for the one-month pre-treatment evaluation baseline. It is clearly advantageous if there is seizure as well as spike suppression as we plan the design of the pivotal trial.

Additional secondary endpoints will be (1) any improvement of cognitive function testing beyond the practice effect (estimated from norms and the improvement in the sham control group); (2) any improvement in quality of life ratings.

Study Monitoring Committee

The safety and comfort decisions for each patient are made by the epileptologist at each site. The safety, comfort, and efficacy of each treatment protocol across sites are reviewed by the Study Monitoring Committee. Vigilance will be maintained throughout the pivotal study to insure safety (no provoked seizures and no adverse effect to non target brain regions). Treatment will be discontinued for any patient that shows treatment-induced seizures, defined as seizures that are not the patient's typical seizures or that occur twice as frequently as the patient's typical seizures, as assessed during baseline. If there are more than five patients with worsening seizures (meeting escape criteria as stated above), the treatment will be suspended at that site. The Study Monitoring Committee (and the FDA when possible) will decide if the trial with that treatment should be terminated at all sites.

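### The memory test and quality-of-life form monitor for unwanted brain change in both directions, but their study-level endpoints count improvement only and lean on a sham group the trial does not have

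*Protocol*

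**What the plan says.** **Safety use.** The Protocol, under Risk of Unwanted Plasticity, accepts that "there is risk of changing plasticity in ways that are unwanted or maladaptive". Under Mitigating the Risk of Unwanted Plasticity it answers with the two instruments. The CVLT is evaluated in each patient, "paying close attention to any changes from the expected improvement in performance with practice from the normative data". The quality-of-life ratings and the seizure diary are gone through with patient and family, "systematically reviewing any complaints or reports that may suggest the treatment is creating unwanted changes in brain function". Monitoring of Risk lists both instruments again at follow-up.

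**Endpoint use.** Secondary Endpoints and Study Success defines the cognitive endpoint as "any improvement of cognitive function testing beyond the practice effect", with that effect "estimated from norms and the improvement in the sham control group". The quality-of-life endpoint is "any improvement in quality of life ratings".

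**Design and schedule.** Clinical Feasibility Trial Design opens with "The goal of this unblinded and uncontrolled (“open-label”) feasibility study" and puts safety first among the things to be evaluated. Follow up Protocol has weekly diary calls "plus a dEEG follow up evaluation session in weeks 2, 4, 8, 16, and 24", with both instruments at each session, and Table 2 agrees. Monitoring of Risk instead places these assessments weekly for three weeks after treatment and then at week 8.

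**Formal safety rules.** Escape Criteria cover discomfort and seizures. The suspension trigger in Monitoring of Risk is a seizure count. The Study Monitoring Committee section also promises vigilance for effects outside the target region, but names no measure for them. None of these rules mentions the CVLT or quality of life.

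**The concern.** The two uses do not match. As a safety monitor, the CVLT is read against an expected practice gain and a departure in either direction counts. As a study-level endpoint, the same score counts only if it exceeds that gain. A patient whose score stays flat where norms predict a rise has lost ground, yet at endpoint level looks the same as a patient on whom stimulation had no effect beyond practice.

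The direction left out is the one named as a risk. The treatment is meant to induce long-term depression of cortex, and the Protocol says its understanding of that manipulation is limited. A small average loss is a group quantity, and the Protocol states no group-level result in which it would show.

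The practice reference matters for the same reason. Under heavy repetition, raw scores may rise even if stimulation does some harm, so the endpoint depends on a sound expectation. Part of the stated expectation comes from a group that does not exist in this study.

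**Working it through.** The Protocol gives no figure to reproduce here: no sample size, SD or effect size for either instrument. The check is one of logic, followed by an illustration under stated assumptions.

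**1. What each use does with the possible truths**

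| True average effect on the CVLT | Per-patient review (Mitigating the Risk of Unwanted Plasticity) | Endpoint (Secondary Endpoints and Study Success) |
|---|---|---|
| Above norm-expected gain | a change, noted | met |
| Equal to expected gain | no change | not met |
| Below expected gain | a change, noted if visible in the individual | not met |

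The last two rows differ in the safety use and coincide in the endpoint.

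**2. Why the practice reference matters.** Let g be the expected practice gain and h the loss due to stimulation. The raw change is g − h. If 0 < h < g, the raw change is positive although the deviation from expectation is −h. Only the deviation shows the loss. With no sham group, g must come from norms alone.

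**3. Repetition.** Baseline Evaluation gives 2 administrations; Table 2 gives 5 at treatment and 5 at follow-up: 2 + 5 + 5 = 12. With the four follow-ups in Monitoring of Risk it is 2 + 5 + 4 = 11. The Protocol does not show that the norms extend to so many repeats.

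**4. Illustration for individuals (assumed shift of 0.5 SD, normal scores).** Share of patients below a cut-off c SD under expectation:

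- No effect: P(Z < −1) = 0.159; P(Z < −1.645) = 0.050.
- Shift of −0.5 SD: P(Z < −0.5) = 0.309; P(Z < −1.145) = 0.126.

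In an assumed 20 patients, the number beyond 1.645 SD is expected to move from 20 × 0.050 = 1.0 to 20 × 0.126 = 2.5. That is hard to recognise one patient at a time.

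**5. Illustration for the group.** One-sample t-test on the deviation from expectation, noncentral t with noncentrality −d√n. The one-sided 0.025 level is borrowed from the spike-rate test in Power Analysis and Missing Data Analysis; the Protocol states no test for these scores. The values of n and d are assumed.

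| n | Decline d (SD) | Improvement-directed test positive | Two-sided 0.05 test flags the decline |
|---|---|---|---|
| 10 | 0.3 / 0.5 / 0.8 | 0.0024 / 0.00035 / 0.00001 | 0.13 / 0.29 / 0.62 |
| 20 | 0.3 / 0.5 / 0.8 | 0.0006 / 0.00002 / below 0.00001 | 0.25 / 0.56 / 0.92 |
| 30 | 0.3 / 0.5 / 0.8 | 0.0002 / 0.000002 / below 0.00001 | 0.36 / 0.75 / 0.99 |

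The half-width of a 95% interval in SD units is t(0.975, n−1)/√n: 2.262/√10 = 0.72, 2.093/√20 = 0.47, 2.045/√30 = 0.37. A two-directional summary can show a decline but will not be precise.

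**6. Chance flags.** With a 1.645 SD cut-off at five follow-ups, an unaffected patient is flagged at least once with probability between 5% (perfectly correlated visits) and 1 − 0.95^5 = 23% (independent visits).

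**The case against.** The strongest reply is that the Protocol does look for decline. Mitigating the Risk of Unwanted Plasticity commits to judging each patient's CVLT against normative practice gains and a pre-treatment baseline, and that wording covers a shortfall. The site epileptologist is responsible for recognising adverse events, and the Study Monitoring Committee reviews safety across sites. A reader might infer that the instruments are analysed only for improvement, or that a decline would be lost from the trial's results. The documents do not support either reading. They do not say that patients are sorted into improved and not improved, they fix no test for these scores, and they do not bar reporting of declines. Nor is the harm a known one: the Protocol calls it a risk and says that the related stimulation literature makes serious unwanted change unlikely.

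It can also be said that benefit endpoints are normally directional. The spike and seizure endpoints here are worded as suppression, with worsening handled under safety. Test details may sit in a statistical analysis plan that is not shown.

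Most of this stands, and it limits the point. But seizure worsening has stated counts and consequences in the safety sections, whereas cognitive and quality-of-life worsening has only individual review, with no stated summary across patients. The endpoint direction is fixed by the Protocol itself, so it is not a detail left for later. The sham-group reference contradicts the stated design however the endpoint is analysed.

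**Conclusion.** The point holds in a limited form. The endpoints on the CVLT and the quality-of-life form are one-directional, they do not match the two-directional safety use of the same instruments, and nothing in the Protocol links the two. A modest average decline therefore cannot be told from no effect in the endpoint results, and individual review is a weak means of finding it. A marked decline in a single patient could still be noticed under the review the Protocol describes. The practice-effect reference to a sham group is a plain contradiction of the uncontrolled design.

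The size in this trial cannot be stated. The percentages of decliners and the detection probabilities rest on assumed shifts of 0.3 to 0.8 SD, assumed samples of 10 to 30, normally distributed deviations and a correct norm-based expectation. The firm result is qualitative: in every scenario tried, an improvement-directed test had a probability of at most about 0.002 of being positive under a true decline, and such a negative result does not separate decline from no effect. This is a worthwhile and inexpensive correction, not a fault that undermines the primary spike endpoint.

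**What to change.** In Secondary Endpoints and Study Success:

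- Define both endpoints as change from baseline in either direction. For the CVLT, use the deviation from the norm-expected retest score. Report a mean with a two-sided 95% interval at each follow-up.
- Delete the reference to a sham group, and state as a limitation that the norms may not cover about 12 administrations.
- Tabulate individual declines descriptively as a safety outcome for the existing Study Monitoring Committee, with a note that repeated testing produces some flags by chance.

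Reconcile this section with Mitigating the Risk of Unwanted Plasticity, and reconcile the follow-up schedules in Follow up Protocol, Monitoring of Risk and Table 2, so that each follow-up has one meaning. No stopping or treatment rule is proposed.

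The cost is revised wording, one table and a check of what the norms cover. No new data are needed. The downside is a little more analysis and wide intervals in a small study.

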There are two studies we found that have examined the effects of a single session of tDCS treatment of the apparent epileptogenic zone (F. Fregni, Thome-Souza, et al., 2006; Rotenberg et al., 2008). Both showed beneficial short term effects of the treatment in suppressing epileptiform discharges, with no increase in seizure frequency.

For the pulsed GTEN protocol emulating the effects of slow rTMS, the literature on seizure risk with slow rTMS in epilepsy is relevant. An important caution is that there have been only a few studies of slow rTMS therapy in epilepsy. Nonetheless, a recent review of the literature for rTMS therapy suggests that there appears to be minimal risk of inducing seizures by the slow rTMS treatment (Bae et al., 2007). The seizures that have been recorded during the slow rTMS treatment session have been the patient's typical seizures in both duration and semiology, suggesting these were not induced by the treatment (Rotenberg et al., 2009).

Thus, for the present feasibility study, the literature suggests the risk of seizures is low. To mitigate the risk, we will monitor carefully for seizures during and after the treatment. During

the three-month pretreatment baseline evaluations, we will characterize the patient's interictal events, plus any ictal events that are recorded, during three two-hour dEEG evaluations. We will train the treatment technician to monitor the EEG for these events during the treatment session. Because the source site of the interictal events is also the presumed epileptogenic zone and the target of the GTEN treatment, this is also the site (and scalp topography) that would be expected to generate seizures if the treatment causes or kindles seizures. The preparation for each patient's treatment will identify not only the source of the epileptiform discharges, but the scalp topography, such that the technician has a select montage (screen arrangement) for the channels that reflect the patient's spikes (and likely seizures).

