During the 17 minute GTEN treatment intervals, the EEG channels that are not used for (source or sink) current delivery will be monitored. The 24 bit ADs of the NA 400 allow adequate dynamic range (± 200 mV) that even channels nearby the current delivery seldom clip. During the rest (resting EEG and break) intervals, all 256 channels will be monitored. For the first ten patients, we will monitor the EEG for three hours following the completion of the treatment; for the rest of the patients we will monitor the EEG for 30 minutes following the completion of treatment.

If there is any increase in epileptiform activity during the treatment or the monitoring interval, interictal or ictal, the consulting epileptologist will review the EEG, the baseline EEGs, and the patient's history to decide if treatment should be discontinued. The patient and if relevant the family will be consulted in this decision.

Risk of Inducing Kindling of Seizures

It is well known that repeated electrical stimulation of the normal mammalian brain may lead to augmenting or progressive kindling of discharges, leading to seizures. Persons with epilepsy may show enhanced cortical excitability that places them at increased risk. In the animal literature, kindling occurs when repeated electrical stimulation of the cortex elicits cortical after-discharges (continuing when the stimulation stops); in some reports the discharges not only lead to seizures, but may lead to epilepsy, with spontaneous discharges and/or seizures in the absence of stimulation (Bertram, 2007).

Mitigating the Risk of Inducing Kindling of Seizures

The same procedures of careful EEG monitoring used to mitigate the risk of seizures will mitigate the risk of kindling. Specifically, the EEG of each patient will be monitored during and after the treatment session, including a specific inspection of the channels near the target site. If the GTEN treatment is observed to lead to any epileptiform discharges that are unlike the patient's typical discharges (spikes) in frequency or localization, the treatment will be discontinued. A specific warning for possible kindling is the observation of repeated discharges that are associated with the repeated application of stimulation, specifically the pulses of the pulsed GTEN protocol. If these are observed, treatment will be stopped.

Risk of Unwanted Plasticity

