- (3) A history or condition of status epilepticus or psychogenic seizures.

- (4) Presence of a cardiac pacemaker, vagus nerve stimulator, or metal implantation in the body (other than the teeth) including neurostimulators, cochlear implants, and implanted medication pumps.
- (5) Previous surgery involving opening the skull.
- (6) Allergy to or condition contraindicating lidocaine.
- (7) Unable to express presence of pain or discomfort.

Escape Criteria

For individual patients, the study will be terminated for any of the following reasons:

- (1) Unacceptable discomfort or pain at stimulation currents of 200 μ A.
- (2) A tonic-clonic seizure occurring during a stimulation session.
- (3) Emergence of a first-in-life tonic-clonic seizure at any time during the study.
- (4) Status epilepticus.
- (5) A two-fold increase of seizure frequency over the baseline seizure frequency. If the frequency of seizures is very low, then an apparent increase during treatment (not reliably quantified as a two-fold increase) will be discussed with the patient, family, physician and Study committee.

The entire study will terminate if 5 subjects meet escape criteria.

Baseline Evaluation

During a one-month pre-treatment baseline evaluation period, the patient (and/or family) will maintain the seizure diary, which will be reviewed by the study coordinator in a phone contact once per week. In addition, two two-hour routine dEEG evaluations will be conducted in the baseline evaluation period, including the opportunity for sleep for patients who may have interictal events in sleep or drowsiness. Each baseline evaluation also includes the California Verbal Learning Test, and the Quality of Life in Epilepsy report.

Probe Treatment and Evaluation

The GTEN Plan is developed to apply current pulses to the epileptic focus, as it is identified from the dEEG source localization of the spike onset. The GTEN Plan will often include more than one treatment option, primarily depending on the orientation of the cortical region identified as the epileptic focus. To evaluate a treatment targeting option, a probe treatment may be conducted, consisting of one 17-min pulsed treatment block (Figure 10) followed by one hour of dEEG evaluation and spike counting. If multiple targeting options are evaluated, the one with the best evidence of spike suppression will be selected for the 5 session treatment intervention.

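### The definition of treatment-induced seizures ignores timing relative to stimulation and gives no comparison window, so a typical non-tonic-clonic seizure during stimulation is left unattributed

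*Protocol*

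**What the plan says.** All references are to the protocol.

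- **Study Monitoring Committee.** Vigilance is to be maintained "to insure safety (no provoked seizures and no adverse effect to non target brain regions"). Treatment is discontinued for a patient with treatment-induced seizures, "defined as seizures that are not the patient's typical seizures or that occur twice as frequently as the patient's typical seizures", judged against baseline.
- **Escape Criteria.** Criterion 2 is "A tonic-clonic seizure occurring during a stimulation session". Criterion 5 is "A two-fold increase of seizure frequency over the baseline seizure frequency"; when seizures are very infrequent, an apparent increase goes to discussion instead. The section adds: "The entire study will terminate if 5 subjects meet escape criteria".
- **Mitigating the Risk of Seizures in Normal Operation.** The treated site is also the site from which seizures would be expected if treatment caused them. The epileptologist reviews "any increase in epileptiform activity during the treatment or the monitoring interval, interictal or ictal". On published slow-rTMS sessions, the section says that recorded seizures "have been the patient's typical seizures in both duration and semiology, suggesting these were not induced by the treatment".
- **Mitigating the Risk of Inducing Kindling of Seizures.** One warning sign that stops treatment is "the observation of repeated discharges that are associated with the repeated application of stimulation". Discharges unlike the patient's usual ones in frequency or localization also end treatment.
- **Review of the EEG for Safety and for Spike Counts; Monitoring of Risk.** The EEG is read after every treatment session. Changed localization, a spike increase above one standard deviation, or atypical seizure activity is passed to the epileptologist. A daily diary is reviewed at each session, again with a two-fold criterion.

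**The concern.** The definition has two routes to the label treatment-induced: unusual form, or doubled frequency. The first is weak by the protocol's own reasoning. Stimulation is aimed at the patient's presumed epileptogenic zone, so a seizure that it provokes may resemble the patient's usual ones. The second depends on how much a few hours of stimulation can move a count taken over a much longer period, and that period is not stated.

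The study is open-label and has no control group. The timing of a seizure, set against the patient's own baseline rate, is therefore among the best evidence on attribution, and the definition does not use it. Safety is the first aim named in the Clinical Feasibility Trial Design section. If typical focal seizures cluster in the stimulation hours, this definition gives the committee no reason to call them induced until the overall frequency doubles. Unless they meet an escape criterion, they also do not count toward the five-subject stop.

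**Working it through.** The protocol attaches no error rate, power or sample size to the definition, so there is no figure of its own to reproduce. The check has three parts.

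**1. Which rule catches which in-session event?**

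| Event during stimulation | Treatment-induced by the definition? | Other rule that applies |
|---|---|---|
| Atypical seizure | Yes | EEG review and escalation |
| Typical tonic-clonic seizure | Only if frequency doubles | Escape criterion 2 |
| Repeated discharges tied to the pulses | Not addressed | Kindling rule stops treatment |
| Typical non-tonic-clonic seizure | Only if frequency doubles | An EEG increase goes to the epileptologist for a treatment decision; no attribution |

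The second row is an inconsistency: the event ends the patient's participation, yet it is not treatment-induced by definition. The last row is the gap. It matters because entry requires partial seizures, with or without secondary generalization.

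**2. How often would a two-fold rule miss a provoked seizure?** The assumptions are Poisson counts, a 30-day month, *b* seizures per month and *k* provoked typical seizures in the treatment week. The values of *b* are illustrative; eligibility runs from two in the last month to fewer than 10 per day.

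- Baseline count X ~ Poisson(*b*), with X > 0.
- Count in a window of *w* days: N = Poisson(*b* × *w*/30) + *k*.
- Missed if N < 2 × X × *w*/30.

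| *b* per month | *k* | Missed, week | Missed, month |
|---|---|---|---|
| 4 | 1 | 46% | 71% |
| 10 | 1 | 75% | 89% |
| 20 | 1 | 88% | 97% |
| 10 | 2 | 58% | 86% |

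The rule is also unspecific: with no effect (*k* = 0) at 4 per month it flags 25% of patients over a week and 21% over a month.

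The window can decide the answer. Take one extra seizure in each of the five sessions:

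- *b* = 15: (15 + 5)/15 = 1.33 over a month, not flagged; (3.5 + 5)/3.5 = 2.43 over the week, flagged.
- *b* = 30: (7 + 5)/7 = 1.71 over the week, not flagged.
- *b* = 4: (4 + 5)/4 = 2.25 over a month, flagged.

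Read per day, one seizure at 10 per month is 1/(10/30) = 3 times baseline and is flagged. So, however, is any chance seizure, and the probability of at least one on a given day is 1 − exp(−10/30) = 28%.

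**3. What would a time-based count show?** Stimulation lasts 5 × 3 × 17 min = 4.25 h (4.17 h if computed from 500 pulses at 0.5 Hz). Expected chance seizures per patient are *b* × 4.25/720: 0.02, 0.06 and 0.12 at 4, 10 and 20 per month.

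For an assumed 10 patients at 10 per month, the expected total is 10 × 10 × 4.25/720 = 0.59. At one-sided 0.025 the critical count is 3, since P(≥3 | 0.59) = 0.022. Power is then:

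- 0.5 provoked per patient: P(≥3 | 5.59) = 92%
- 0.2 per patient: P(≥3 | 2.59) = 48%
- 0.1 per patient: P(≥3 | 1.59) = 21%

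With no seizure observed, the exact 97.5% upper bound is −ln(0.025) = 3.69 seizures, or 3.69/0.59 = 6.2 times expected.

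**The case against.** The definition sits inside a discontinuation rule. A reader might infer that the study would declare no provoked seizures whenever this definition is not met, while typical seizures are being provoked. The documents do not support that. The phrase about provoked seizures is an aim of vigilance, in a sentence that speaks of the pivotal study. It is not an endpoint, a test or a reporting rule. The stated criterion for moving on is spike suppression.

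A reader might also infer that the protocol ignores in-session timing altogether. It does not. Escape criterion 2 and the pulse-associated stop are both tied to stimulation, increases on the session EEG go to the epileptologist, every session's EEG is read, and criterion 5 provides for discussion when seizures are rare. The remark on typical semiology describes published rTMS sessions and is not this trial's attribution rule.

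The miss rates rest on windows chosen here. A daily reading, which the daily diary could support, would flag a single seizure at 4 or 10 per month. The 92% power likewise depends on an assumed 10 patients and a large effect. An observed-versus-expected table could also stand in an analysis plan that is not shown, so its absence from the protocol is no finding.

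All of this stands, and it limits the point to the definition. None of these rules attributes a typical non-tonic-clonic seizure during stimulation to treatment, and the missing window is itself part of the defect.

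**Conclusion.** The concern holds in limited form. The only definition of a treatment-induced seizure has no timing element and no comparison window, and it does not match escape criterion 2 or the session rules. Typical non-tonic-clonic seizures in session have no attribution rule short of a doubling. Counted over a week or a month, a doubling would often fail to register one or two such events: about 46% and 71% missed at 4 per month and 75% and 89% at 10 per month, for one provoked seizure. These figures assume Poisson counts and illustrative rates. They do not carry over to a daily window, and at low baseline rates the rule can trigger when several seizures are provoked. The point concerns attribution and safety reporting. It does not show that in-session seizures would go unnoticed or unmanaged.

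**What to change.** The sponsor should reconcile the two risk-mitigation sections on seizures and kindling, Escape Criteria, Study Monitoring Committee, and the EEG review and Monitoring of Risk sections, and should state the comparison window for the two-fold criterion. Which stopping or discontinuation rule should apply is for the sponsor; none is proposed here.

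Separately, for safety reporting only:

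- Count every seizure of any type during stimulation blocks and, separately, in the post-session monitoring window.
- Show clinical and EEG-only events separately.
- Compare each count with the expected number (each patient's baseline diary rate times the hours, summed over patients), and report the observed-to-expected ratio with an exact Poisson upper confidence bound.
- Do not base a statement of no provoked seizures on the existing definition alone.

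The cost is wording and one calculation; the sessions are already EEG-monitored and the diary is already kept. There are three downsides. The safety statement may be less favourable. Diary rates miss subclinical events, and they may understate the expected count when treatment is given in sleep, as the Treatment Protocol section allows. Precision is limited in a small study, as the power of 48% and 21% for smaller effects shows.
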